### **8.3 Emergency unblinding of treatment assignment**

Not applicable.

### **8.4 Pregnancies**

To ensure patient safety, each pregnancy occurring while the patient is on study treatment must be reported to Novartis within 24 hours of learning of its occurrence. The pregnancy should be followed up to determine outcome, including spontaneous or voluntary termination, details of the birth, and the presence or absence of any birth defects, congenital abnormalities, or maternal and/or newborn complications.

Pregnancy should be recorded on a Clinical Trial Pregnancy Form and reported by the investigator to the Novartis DS&E. Pregnancy follow-up should be recorded on the same form and should include an assessment of the possible relationship to the study drug for any pregnancy outcome. Any SAE experienced during pregnancy must be reported on the SAE Report Form.

Pregnancy outcomes must be collected for the female partners of any males who took study treatment in this study. Consent to report information regarding these pregnancy outcomes should be obtained from the mother.

Preclinical data regarding reproductive toxicity is described in the most recent IB. The potential reproductive risk for humans is unknown. Women of childbearing potential should be advised to use highly effective contraception methods while they are receiving everolimus and up to 8 weeks after treatment has been stopped. If a pregnancy occurs while on study treatment, the newborn will be followed for at least 12 months.

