### **5.3 Exclusion criteria**

Patients eligible for this study must not meet **any** of the following criteria:

1. Patient has been permanently discontinued from everolimus study treatment in the parent study.
2. Sexually active males, unless they use a condom during intercourse while taking drug and for 8 weeks after stopping study medication. Males also should not father a child in this period. A condom is required to be used also by vasectomized men in order to prevent delivery of the drug via seminal fluid.
3. Pregnant or nursing (lactating) women, where pregnancy is defined as the state of a female after conception and until the termination of gestation, confirmed by a positive hCG laboratory test.
4. Women of child-bearing potential, defined as all women physiologically capable of becoming pregnant, unless they are using highly effective methods of contraception during dosing and for 8 weeks after everolimus last dose. Women are considered post-menopausal and not of child-bearing potential if they have had 12 months of natural (spontaneous) amenorrhea with an appropriate clinical profile (e.g. age appropriate, history of vasomotor symptoms) or have had surgical bilateral oophorectomy (with or without hysterectomy) or tubal ligation at least six weeks prior to randomization. In the case of oophorectomy alone, only when the reproductive status of the woman has been confirmed by follow up hormone level assessment is she considered not of child-bearing potential

Highly effective contraception methods include:

- Total abstinence (when this is in line with the preferred and usual lifestyle of the subject. Periodic abstinence (e.g., calendar, ovulation, symptothermal, post-ovulation methods) and withdrawal are not acceptable methods of contraception)
- Female sterilization (have had surgical bilateral oophorectomy with or without hysterectomy) or tubal ligation at least six weeks before taking study treatment. In case of oophorectomy alone, only when the reproductive status of the woman has been confirmed by follow up hormone level assessment
- Male sterilization (at least 6 months prior to screening). For female subjects on the study the vasectomized male partner should be the sole partner for that subject.

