- Use of oral, injected or implanted hormonal methods of contraception or placement of an intrauterine device (IUD) or intrauterine system (IUS), or other forms of hormonal contraception that have comparable efficacy (failure rate <1%), for example hormone vaginal ring or transdermal hormone contraception.
- In case of use of oral contraception women should have been stable on the same pill for a minimum of 3 months before taking study treatment.

If a study patient or partner becomes pregnant or suspects being pregnant during the study or within 30 days after the last dose of everolimus, the investigator needs to be informed immediately and ongoing study treatment with everolimus has to be stopped immediately.

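### The protocol's pregnancy windows disagree (on treatment in 8.4, 30 days in 5.3, 8 weeks of contraception in both), so a female patient's pregnancy beginning after the last dose may not be reported

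*Protocol*

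**What the plan says.** Three different periods attach to pregnancy in the protocol.

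- **Reporting to the sponsor (8.4).** "each pregnancy occurring while the patient is on study treatment must be reported" to the sponsor, within 24 hours of the site becoming aware of it. The rule that a newborn is followed for at least 12 months has the same on-treatment trigger.
- **Notice to the investigator (5.3).** For a pregnancy in a patient or partner during the study or "within 30 days after the last dose of everolimus, the investigator needs to be informed immediately".
- **Contraception (5.3 and 8.4).** Women must be "using highly effective methods of contraception during dosing and for 8 weeks after everolimus last dose". Section 8.4 repeats the period: "while they are receiving everolimus and up to 8 weeks after treatment has been stopped". Sexually active men are excluded "unless they use a condom during intercourse while taking drug and for 8 weeks after stopping study medication", and they are told not to father a child in that time.

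Other sections bear on the point:

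- 8.1.3 lists pregnant or breast-feeding women among the potential risks to be reported on the SAE form. It sets no period of its own.
- 8.2.2 requires SAE reporting until at least 30 days after treatment stops, and afterwards only if the investigator suspects causality.
- 8.4 requires pregnancy outcomes to be collected for partners of treated men, with no time limit.
- 7.2.2 places the last pregnancy test at the End of Treatment visit. 7.1.5 places the last contact at 30 days.

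The SAP does not address pregnancy.

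**The concern.** Long-term safety is the study's only objective (Table 3-1). Section 8.4 states that the human reproductive risk is unknown, and 8.1.3 puts postnatal development toxicity, pregnancy and male infertility on the list of risks to be reported. Pregnancies should be few in this population, so each one lost matters.

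With three periods for one subject, two sites could treat the same case differently. One could report a pregnancy that began two weeks after the last dose. Another could note it locally and, relying on the on-treatment wording of 8.4, send nothing and arrange no newborn follow-up. For a pregnancy beginning in the second month after stopping, the patient is still within the required contraception period, yet no section plainly tells the site to report it.

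**Working it through.** The plan gives no figure to reproduce. The check sets the periods on one time scale, in days after the last everolimus dose.

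**Lengths**

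- Contraception period: 8 × 7 = 56 days (5.3, 8.4).
- Days after the last dose covered by the explicit 24-hour trigger in 8.4: 0 of 56.
- Days covered by notice to the investigator in 5.3: 30 of 56.
- Remainder: 56 − 30 = 26 days (days 31 to 56); 26/56 = 46%.

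**Which duty applies to a female patient's pregnancy, by when it begins**

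| Pregnancy begins | 5.3: inform investigator | 8.4: 24-hour report and newborn follow-up | 8.1.3 with 8.2.2: SAE form |
|---|---|---|---|
| On treatment | Yes | Yes | Yes |
| Days 1–30 | Yes | Outside the explicit trigger | Arguably, through the list in 8.1.3 |
| Days 31–56 | No | Outside the explicit trigger | Only if treated as an SAE with suspected causality |

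**Partners of male patients.** Section 8.4 collects outcomes with no cut-off, so the outcome gap mainly concerns female patients. Section 5.3 still stops notification of a partner's pregnancy at 30 days, so the two sections differ here too.

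**How much drug could be present.** The Pharmacokinetics text in 1.2.1.2 gives an average terminal half-life of 30 hours. Assuming simple exponential decline, the fraction left is 0.5^(hours/30):

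- day 1: 0.5^(24/30) = 0.5^0.8 = 0.57
- day 7: 0.5^(168/30) = 0.5^5.6 = 0.02
- day 30: 0.5^(720/30) = 0.5^24 = 6 × 10⁻⁸

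Residual drug is therefore concentrated in the first days after stopping. Those days lie outside the explicit 8.4 trigger although 5.3 sends their pregnancies to the investigator. By day 31 the residual is negligible on this calculation.

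**Chance of detection.** After the End of Treatment test no pregnancy test is scheduled. The 30-day contact asks about adverse events, and no study visit follows. Later pregnancies come to light only if someone volunteers them.

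**The case against.** The strongest reply is that 8.4 should not be read alone.

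- **The SAE-form route.** 8.1.3 carries no on-treatment limit and, read with 8.2.2, gives a route for days 1 to 30. The second paragraph of 8.4 also says, without a date, that pregnancies are to be recorded and sent to the sponsor's safety department. This stands in part: it would be wrong to say that only on-treatment pregnancies can be reported, or that all 56 days lack any route. But the list entry names a group of patients rather than an event, and the undated sentence follows a paragraph limited to pregnancies on treatment. A site could reasonably take either as no wider than that.
- **Late detection.** 8.4 depends on when the pregnancy occurs, and the 24 hours run from learning of it. A pregnancy conceived on treatment and found later is already reportable. This stands.
- **Adverse outcomes.** A congenital anomaly is an SAE (8.2.1), 8.4 requires any SAE during pregnancy to be reported, and SAEs after 30 days remain reportable where causality is suspected. This stands, but a causality condition is a weak filter when the human risk is stated to be unknown.
- **Matching the windows.** A contraception period may include a margin, and 30 days matches the protocol's general safety follow-up. A reporting period need not equal a contraception period. That is fair, but it does not explain why 5.3 and 8.4 differ from each other.

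A reader might also infer that the protocol declares an 8-week reproductive-risk window and that pregnancies on days 31 to 56 are drug-exposed. The documents support neither. Eight weeks is given as a contraception period, and the stated half-life leaves almost no drug by day 30.

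**Conclusion.** The inconsistency is real and worth correcting. For female patients, pregnancies beginning on days 1 to 30 fall outside the explicit reporting and newborn follow-up trigger and depend on an ambiguous list. Those beginning on days 31 to 56 have no explicit duty apart from the conditional SAE route. The 46% is a share of calendar days; it does not estimate missed pregnancies or exposure, and the documents give no basis for such an estimate. The earlier interval matters more, because that is where residual drug could be present.

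The conclusion assumes that being on study treatment ends with the last everolimus dose. Section 6.1 also counts combination drugs as study treatment, so a patient still taking one might be read as on treatment. The pharmacokinetic remark assumes that the average half-life applies.

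This is a gap in safety data collection. No analysis set, endpoint or statistical figure changes.

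**What to change.** Reconcile 5.3, 8.1.3 and 8.4 on one stated period:

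1. In 8.4, apply 24-hour reporting to the sponsor, outcome follow-up and newborn follow-up to any pregnancy the site learns of that begins between first dose and the end of the protocol's own post-dose contraception period. Keep the existing collection of partner outcomes, which has no time limit.
2. In 5.3, change the 30-day notification wording, for patients and partners, to the same period.
3. In 8.1.3, reword the list entry as an event and refer to 8.4 for its period.
4. At the existing 30-day contact (7.1.5), tell patients to report a pregnancy up to that end date. Put the same statement in the consent text.

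The cost is a few sentences in an amendment, matching consent wording and a few more pregnancy forms. No visit or test is added. The limit of the change is that pregnancies after the 30-day contact will be captured only if the patient reports them, and the protocol should say so.

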## **8.5 Warnings and precautions**

No evidence available at the time of the approval of this study protocol indicated that special warnings or precautions were appropriate, other than those noted in the provided IB. Additional safety information collected between IB updates will be communicated in the form of IN. This information will be included in the patient informed consent and should be discussed with the patient during the study as needed.

## **8.6 Data Monitoring Committee**

Not applicable.

## **8.7 Steering Committee**

Not applicable.

# **9 Data collection and management**

## **9.1 Data confidentiality**

Information about study subjects will be kept confidential and managed under the applicable laws and regulations. Those regulations require a signed subject authorization informing the subject of the following:

- What protected health information (PHI) will be collected from subjects in this study
- Who will have access to that information and why
- Who will use or disclose that information
- The rights of a research subject to revoke their authorization for use of their PHI.

In the event that a subject revokes authorization to collect or use PHI, the investigator, by regulation, retains the ability to use all information collected prior to the revocation of subject authorization. For subjects that have revoked authorization to collect or use PHI, attempts should be made to obtain permission to collect follow-up safety information (e.g. has the subject experienced any new or worsened AEs) at the end of their scheduled study period.

The data collection system for this study uses built-in security features to encrypt all data for transmission in both directions, preventing unauthorized access to confidential participant information. Access to the system will be controlled by a sequence of individually assigned user identification codes and passwords, made available only to authorized personnel who have completed prerequisite training.

## **9.2 Site monitoring**

Before study initiation, at a site initiation visit or at an investigator's meeting, Novartis personnel [or designated contract research organization (CRO)] will review the protocol and eCRFs with the investigators and their staff. During the study, the field monitor will visit the site regularly to check the completeness of patient records, the accuracy of entries on the eCRFs, the adherence to the protocol to Good Clinical Practice, the progress of enrollment, and to ensure that everolimus is being stored, dispensed, and accounted for according to specifications. Key study personnel must be available to assist the field monitor during these visits.

The investigator must maintain source documents for each patient in the study, consisting of case and visit notes (hospital or clinic medical records) containing demographic and medical information, laboratory data, electrocardiograms, and the results of any other tests or assessments. All information recorded on eCRFs must be traceable to source documents in the patient's file. The investigator must also keep the original signed informed consent form (ICF) (a signed copy is given to the patient).

The investigator must give the monitor access to all relevant source documents to confirm their consistency with the eCRF entries. Novartis monitoring standards require full verification for the presence of informed consent, adherence to the inclusion/exclusion criteria and documentation of AEs. Additional checks of the consistency of the source data with the CRFs are performed according to the study-specific monitoring plan.

### **9.3 Data collection**

For studies using Electronic Data Capture (EDC), the designated investigator staff will enter the data required by the protocol into the eCRF. The eCRFs have been built using fully validated secure web-enabled software that conforms to 21 CFR Part 11 requirements. Investigator site staff will not be given access to the EDC system until they have been trained. Automatic validation programs check for data discrepancies in the eCRFs and, allow modification or verification of the entered data by the investigator staff.

The Principal Investigator (PI) is responsible for assuring that the data entered into eCRF is complete, accurate, and that entry and updates are performed in a timely manner.

### **9.4 Database management and quality control**

For studies using eCRFs, Novartis personnel (or designated CRO) will review the data entered by investigational staff for completeness and accuracy. Electronic data queries stating the nature of the problem and requesting clarification will be created for discrepancies and missing values and sent to the investigational site via the EDC system. Designated investigator site staff are required to respond promptly to queries and to make any necessary changes to the data.

The occurrence of any protocol violations will be determined. After these actions have been completed and the data has been verified to be complete and accurate, the database will be declared locked and made available for data analysis. Authorization is required prior to making any database changes to locked data, by joint written agreement between the Global Head of Biostatistics and Data Management and the Global Head of Clinical Development.

For EDC studies, after database lock, the investigator will receive a CD-ROM or paper copies of the patient data for archiving at the investigational site.

## **10 Statistical methods and data analysis**

Statistical analysis will be performed when all patients discontinued the trial or the 30-day safety follow-up was completed, whichever comes earlier. Those analyses results will be used to document the summary of the safety.

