Study design	
This is a multi-center, open label study to collect and assess long-term safety of everolimus in patients being treated in current Novartis-sponsored studies and who are benefiting from treatment with everolimus judged by the investigator. There will be no screening period for this study. Eligible patients are to be consented and can start their treatment with everolimus as soon as they enter the study.
 
At least, patients must return to the study center on a yearly basis (<math>\pm</math> 3 months), but for resupply of study medication, the frequency of the receipt and dispensing must follow local practice (e.g., every 2 to 3 months). At this time the dose of everolimus is based on the investigator's judgment.
 
Adverse events (AEs) will be collected continuously throughout the study. For the safe and effective use of everolimus, patient may return to the clinic at any given time following local practice. When AEs are observed, additional visits will be arranged by investigator's discretion.
 
Patients will continue to be treated until they are no longer benefiting from everolimus as defined in the parent protocol (disease progression), develop unacceptable toxicities, withdraw consent, are non-compliant to the protocol, the investigator feels it is no longer in the patient's best interest to continue everolimus therapy or the patient dies, whichever comes first.
 
A patient will reach the end of study when everolimus treatment is permanently discontinued and the end of treatment visit has been performed. All patients must be followed for AEs for 30 days after the last dose of everolimus.
 
The study is expected to remain open for 5 years or until such time that enrolled patients no longer need treatment with everolimus, whichever comes first.

Population	Male and female patients, who are currently enrolled in a Novartis-sponsored everolimus study, are benefiting from treatment with everolimus and have fulfilled all their requirements in the parent study.
Inclusion criteria	
Patient is currently enrolled in a Novartis- sponsored everolimus study, receiving everolimus and has fulfilled all their requirements in the parent study.
 
Patient is currently benefiting from the treatment with everolimus, as determined by the guidelines of the parent protocol.
 
Patient has demonstrated compliance, as assessed by the investigator, with the parent study protocol requirements.

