Exclusion criteria	Patient has been permanently discontinued from everolimus study treatment in the parent study due any reason.
Investigational and reference therapy	Everolimus, 2.5 – 10 mg/day.
Efficacy assessments	Not applicable

Safety assessments	Reported AEs will be collected continuously throughout the study. For the safe and effective use of everolimus, medical monitoring should be performed as clinically indicated at the physician's discretion.
Other assessments	Not applicable
Data analysis	Statistical analysis will be performed when all patients discontinued the trial or the 30-day safety follow-up was completed, whichever comes earlier. Those analyses results will be used to document the summary of the safety. Data will be used only for descriptive summary of patients remaining on drug.
Key words	Everolimus, roll-over study

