## 4.3 Definition of end of the study

The end of the study is defined as when the patient permanently discontinues treatment with everolimus and the end of treatment visit has been performed for each patient.

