### **7.1.4 End of treatment visit including study completion and premature withdrawal**

Patients will continue to be treated until they are no longer benefiting from everolimus treatment, develop unacceptable toxicities, withdraw consent, are non-compliant to the protocol, or the patient dies, whichever comes first.

At the time the patient discontinues study treatment, a visit should be scheduled as soon as possible, at which time the End of Treatment visit will be performed. End of Treatment information will be completed in the eCRF giving the date and reason for stopping the study treatment.

At a minimum, all patients who discontinue study treatment, including those who refuse to return for a final visit, will be contacted for the required safety evaluation during the 30 days after the last dose of everolimus.

Patients who discontinue study treatment should be considered withdrawn from the study after the final visit assessments are performed or when it is clear that the patient will not return for these assessments.

If a study withdrawal occurs, or if the patient fails to return for visits, the investigator must determine the primary reason for a patient's withdrawal from the study and record this information on the appropriate eCRF page.

A patient will reach the end of study when everolimus treatment is permanently discontinued and there will be **no** further follow-up study visits. Thirty-day safety follow-up could be done via a phone contact.

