### **7.1.5 Follow up for safety evaluations**

All patients must be followed up for safety evaluations for 30 days after the last dose of everolimus. At the end of this period, the investigator should contact the patient to inquire about any AE observed during this period. This could be done via a phone contact. Following this there are **no** further follow-up study visits.

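### The only analysis is timed at the earlier of trial discontinuation and completed 30-day follow-up, so the primary AE tables may be run before the 30-day post-dose window closes

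*Protocol*

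**What the plan says.** Section 10 of the protocol schedules the statistical analysis "when all patients discontinued the trial or the 30-day safety follow-up was completed, whichever comes earlier". The same sentence stands in the Data analysis row of the Protocol summary and in SAP Section 1. Section 4.2 gives interim analyses as not applicable, and no other analysis is described.

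A patient's end of study is described in two ways:

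- Sections 4.1, 6.1.5 and 7.1.4 place it at permanent discontinuation of everolimus.
- The Study design row of the summary adds a visit: "A patient will reach the end of study when everolimus treatment is permanently discontinued and the end of treatment visit has been performed". Section 4.3 defines the end of the study in the same terms: "when the patient permanently discontinues treatment with everolimus and the end of treatment visit has been performed for each patient".

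Section 7.1.4 asks for the End of Treatment visit promptly after stopping and adds: "Patients who discontinue study treatment should be considered withdrawn from the study after the final visit assessments are performed", or once it is clear that the patient will not return. The later safety contact is separate: "Thirty-day safety follow-up could be done via a phone contact". It is mandatory under Section 7.1.5: "All patients must be followed up for safety evaluations for 30 days after the last dose of everolimus".

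The primary endpoint in Table 3-1 is the frequency and nature of AEs. Protocol 10.4.1 and SAP 1.2 run the on-treatment period to 30 days after the last dose. Protocol 10.4.2 and SAP 1.2.1 tabulate the AEs that start or worsen in that period.

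**The concern.** The tables are defined over a window that the analysis trigger does not wait for. If a patient has discontinued the trial once everolimus has stopped and the End of Treatment visit is done, the first condition can be met for all patients while the last of them are still inside their 30 days. The earlier-of wording then lets the analysis go ahead.

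The AEs in question would still be collected, because the 30-day contact is mandatory. This also holds after early termination, since Section 4.4 sends those patients to the Section 7.1.4 assessments. The risk is that the primary tables are produced without these events and so understate AE incidence for the last patients to stop. Few patients would be affected if stops are staggered. Many could be if the study closes at about 5 years or the sponsor ends it and patients stop together.

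**Working it through.** The documents give no sample size, event rate or lock schedule, so there is no planned figure to reproduce. The check has two parts.

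**1. Can the first condition precede day 30?**

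- If discontinuing the trial means stopping everolimus (4.1, 6.1.5, 7.1.4), it falls on day 0 of the window. The last patient's discontinuation then always precedes the end of that patient's follow-up, so the follow-up condition can never determine the date.
- If it also needs the End of Treatment visit (summary, 4.3), it falls on the day of that visit, which is requested promptly and so normally before day 30.
- No section makes completed 30-day follow-up a condition of lock or analysis. Section 9.4 sets a general requirement: "After these actions have been completed and the data has been verified to be complete and accurate, the database will be declared locked". Sections 9.3 and 11.6 ask for complete entry. None of them names the 30-day contact.

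So the first condition can come first under either end-of-study description.

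**2. How much of the window can be lost?**

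Let d be the days from a patient's last dose to the trigger, and L the days from trigger to lock. Neither is in the documents.

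Unobserved days: g = max(0, 30 − d − L)

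A patient who stopped s days before the last patient has d larger by s. With the trigger and lock on the day the last patient stops, a patient who stopped 10 days earlier loses 30 − 10 = 20 days, and one who stopped 30 or more days earlier loses none.

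SAP 1.2.1 reports the number and percentage of patients by preferred term, maximum severity and relationship. A table therefore changes only if a new term, a higher grade or a changed relationship falls in the gap. For an assumed constant rate r of such events per patient-year:

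Chance of at least one in the gap = 1 − exp(−r × g / 365.25)

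| d + L (days) | g (days) | r = 0.5 | r = 1 | r = 2 |
|---|---|---|---|---|
| 0 | 30 | 4.0% | 7.9% | 15.1% |
| 7 | 23 | 3.1% | 6.1% | 11.8% |
| 14 | 16 | 2.2% | 4.3% | 8.4% |
| 21 | 9 | 1.2% | 2.4% | 4.8% |
| 28 | 2 | 0.3% | 0.5% | 1.1% |
| 30 or more | 0 | 0 | 0 | 0 |

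Example: g = 30 and r = 1 give 1 − exp(−30/365.25) = 1 − exp(−0.0821) = 7.9%.

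The top row needs trigger and lock on the day of the last dose, so it is a ceiling and not an expectation. If the analysis instead waits for completed follow-up, g = 0 for every patient who can be followed.

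**The case against.** The strongest reply is that the sentence was meant patient by patient: each patient has either left the trial and cannot be followed, or has completed 30 days. That reading gives both conditions a purpose, and Section 7.1.4 does recognise patients who will not return. It may well be the intention. But the sentence speaks of all patients and takes the earlier event, which does not say this, and Sections 4.1, 6.1.5 and 7.1.4 tie the end of study to stopping everolimus. If the per-patient rule was meant, it should be written.

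Second, a database without a mandatory contact is hard to call complete, and queries and verification before lock take time. This stands as a practical safeguard, and d + L may well reach 30 days. It remains an unstated link: Section 9.4 concerns the verification of entered data and does not override the stated trigger. After lock, Section 9.4 requires joint written agreement at senior level for any change, so late AEs would be awkward to add.

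Third, the study is descriptive, without a hypothesis test or a formal sample size, and Section 8.2.2 still requires SAEs to be reported within 24 hours for at least 30 days after treatment stops. This limits the consequence to the descriptive tables, but those tables are the whole primary analysis.

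Finally, SAP 1.1.4 defines the last dose for the exposure calculation only, while the follow-up sections count from the last dose of everolimus. For a patient who continues everolimus outside the study, these could differ. The point is minor, because Protocol 10.4.1 and SAP 1.2 anchor the AE window to study medication.

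**Conclusion.** The concern holds. As written, the rule allows the only analysis to be run before the AE window closes for patients who stop within 30 days of database lock. The loss is at most 30 days per affected patient and zero once d + L reaches 30. Over the assumed rates of 0.5 to 2 table-changing events per patient-year, the chance per affected patient is 4.0% to 15.1% at the ceiling, 2.2% to 8.4% with a 16-day gap and 0.3% to 1.1% with a 2-day gap. These figures rest on assumed d, L and r, and the number of affected patients cannot be estimated. Confidence is high that the wording permits early tables; whether it would happen depends on lock practice. The point should be fixed, because it touches the sole primary endpoint and the correction costs little.

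**What to change.** Replace the timing sentence in the Protocol summary, Protocol Section 10 and SAP Section 1 with:

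> The analysis will be run after every patient has stopped everolimus supplied under this protocol and has either completed the 30-day safety follow-up or definitively cannot complete it (death, withdrawal of consent, loss to follow-up).

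Referring to everolimus supplied under this protocol covers patients who continue the drug elsewhere, and matches SAP 1.1.4, which takes the last dose from this protocol's database.

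Two alignments follow:

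- SAP 1.1.2 counts patients still ongoing at the analysis. Under this trigger there are none, so delete the count or state that it is zero by design. Keep the summary of the primary reason for end of treatment.
- The summary's Data analysis row says: "Data will be used only for descriptive summary of patients remaining on drug". This can be read as limiting the summary to patients still on drug, or as describing who was enrolled. Refer instead to the analysis sets in Section 10.1.

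The cost is one sentence in three places, one phrase in SAP 1.1.2 and one sentence in the summary. The analysis moves by about 30 days at most. No new data are needed, because the follow-up is already required.
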